5.4.3. Quality of Life Questionnaires

5.4.3.1. Migraine Specific Quality of Life (MSQ) v2.1

Migraine Specific Quality of Life (MSQ) v2.1 consists of 14 questions. The questions measure the impact of migraine on health-related quality of life across 3 domains: 1) Role Function-Restrictive (7 questions), examines the degree to which performance of daily activities is limited by migraine; 2) Role Function-Preventive (4 questions), examines the degree to which performance of daily activities is prevented by migraine; 3) Emotional Function (3 questions), examines feelings of frustration and helplessness due to migraine.

Precoded item values and final item values for each MSQ item response are shown in Table 5.3. All item values range from 1 to 6. Final item value will be used as for analysis with higher score reflecting better quality of life.

Table 5.3. Item Values for Migraine Specific Quality of Life (MSQ) Item Responses

Response Categories	Precoded Item Value	Final Item Value
None of the time	1	6
A little bit of the time	2	5
Some of the time	3	4
A good bit of the time	4	3
Most of the time	5	2
All of the time	6	1

Questions 1 to 7 of the questionnaire will be grouped together as Role Function-Restrictive domain, questions 8 to 11 as Role Function-Preventive domain and questions 12 to 14 as the

Emotional Function domain. In general, no imputation for missing values is necessary because the MSQ was collected using patient direct data entry on an electronic device which did not allow patients to skip items. Patient either completed the scale in its entirety or not at all.

The raw score of each domain will be calculated as the sum of the raw scores of each question in that domain, using imputed scores where applicable. Should it be the case that the number of missing responses was more than half the questions in that domain, meaning that imputation of missing scores will not be done, the raw score for that domain will not be calculated, hence missing.

The total score of all 3 domains will be calculated as the sum of raw scores of 3 domains. If any of the 3 domain scores is missing, then total score will be missing.

In addition, the raw scores of each domain and the total score will be transformed to a 0 to 100 scale using the following formulae:

• Role Function-Restrictive (range of 7 to 42):

$$\frac{(\text{raw score} - 7)\text{x}100}{35}$$

• Role Function-Preventive (range of 4 to 24):

$$\frac{(\text{raw score} - 4)x100}{20}$$

• Emotional Function (range of 3 to 18):

$$\frac{(\text{raw score} - 3)x100}{15}$$

• Total Score (range of 14 to 84):

$$\frac{(\text{raw total score} - 14) \times 100}{70}$$

If any of the Role Function-Restrictive, Role Function-Preventive or Emotional Function domain is missing, then the total score will be missing, otherwise, the total score will be calculated as the sum of Role Function-Restrictive, Role Function-Preventive, and Emotional Function domain scores.

Responders in Role Function-Restrictive will be derived as outlined in "Statistical Analysis Plan for Psychometric Properties of the MSQ v2.1 Role Function-Restrictive Domain."

5.4.3.2. MIDAS (Migraine Disability Assessment) Questionnaire

The Migraine Disability Assessment questionnaire (MIDAS) consists of 5 questions (Q1-Q5) and 2 additional questions (A and B). The questionnaire measures the impact that migraine headaches have on migraineurs' life, including days of work or school missed, days with

productivity at work or school reduced to half or more, days with household work missed, days with productivity in household work reduced to half or more, and days missed family / social / leisure activities. Each question is answered as a numeric number of days during the past 3 months of assessment, ranging from 0 to 90. The answers to all 5 questions will be added up to a total MIDAS score. No imputation is needed when calculating the total score as patients are not allowed to send partial data.

The MIDAS responders are defined as patients with >50% improvement in the total MIDAS score.

The total MIDAS score, the raw score of each question, and the indicator of MIDAS responders will be used as analysis values.

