# 9.4.2. Key Secondary Analyses

The key secondary objectives (see Table CGAH.1) will be tested using an appropriate multiple testing approach providing strong control of the familywise error rate (for the primary and key secondary tests) at a one-sided 0.025 alpha level (or, equivalently, two-sided 0.05 alpha level).

There will be no adjustments for multiplicity for analyses of other endpoints. If the multiple testing approach for key secondary measures only needs to be changed, the updated approach will be provided in the SAP, and it should not lead to modification of this protocol.

The key secondary measures will be analyzed for the double-blind treatment (Study Period III).

For the continuous key secondary measures, the change from baseline during the 6-month double-blind treatment phase will be analyzed from repeated measures analyses as described in Section 9.4.1. For the analysis of 50%, 75%, and 100% response, the percentage of patients meeting response criteria during the 6-month double-blind treatment phase will be estimated for each treatment from a categorical, pseudo-likelihood-based repeated measures analysis of longitudinal binary outcomes indicating whether patients meet response criteria.

This analysis will be implemented using the GLIMMIX procedure in SAS.

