4.3. Exploratory Objectives

Table 4.3. List of Exploratory Objectives and Their Endpoints

Objectives	Endpoints		
CCI			
To explore the effect of LY2951742 on non-migraine chronic pain	Mean change from baseline in average pain severity of other chronic pain conditions.		
To compare LY2951742 with placebo with respect to categorical changes in quality of life	Percentages of patients with • ≥50% improvement in MIDAS total score • change from baseline in MSQ Role Function-Restrictive ≥10.9 • change from baseline in MSQ Role Function-Preventive ≥8.3 • change from baseline in MSQ Emotional Function ≥12.2		
To compare LY2951742 with placebo with respect to the proportion of migraine headache days requiring medication for the acute treatment of migraine or headache	Change from baseline in the proportion of monthly migraine headache days requiring medication for the acute treatment of migraine or headache		
To compare LY2951742 with placebo with respect to changes in symptomatology associated with migraine or probable migraine	Change from baseline in the number of monthly migraine headache days with nausea and/or vomiting photophobia and phonophobia aura prodromal symptoms other than aura		

5. A Priori Statistical Methods

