5.2. Determination of Sample Size

The study will enroll approximately 825 patients. Eligible patients will be randomized in blinded fashion in a 2:1:1 ratio to placebo (approximately 413 patients), LY2951742 120 mg/month (target of 206 patients), or 240 mg/month (target of 206 patients). With the assumption of a 26% discontinuation rate and an effect size of 0.33 in the last month of the 6-month treatment phase, it is estimated that this sample will provide approximately 95% power that at least 1 dose of LY2951742 will separate from placebo at a one-sided 0.025 significance level based on simulations using Dunnett test. Assumptions were based on data from 2 double-blind, placebo-controlled, Phase 2 studies, with adjustment to reflect the longer treatment duration and greater variability expected in a larger, multi-country, Phase 3 study.

^aPatients randomized to the 120 mg dose will receive a loading dose of 240 mg at the first injection only (Visit 3). Abbreviations: SP = study period.

Approximately 1557 patients may be screened to ensure randomization of 825 patients, with an estimated 611 patients completing the study.

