5.5.11. Quality-of-Life (QoL) Analyses

The mean change from baseline to each post-baseline visit for Study Period III and Study Period III/IV for MIDAS (item scores and total score), I as defined in Section 5.4.3 will be evaluated using MMRM as described in Section 5.5.10.1.

The mean change from baseline to each post-baseline visit for Study Period III and Study Period III/IV for MSQ total score and domain scores averaged across Months 4-6 will be evaluated using MMRM as described in Section 5.5.10.1. The endpoint for comparing LY2951742 with placebo will be estimated using a LSMESTIMATE statement in PROC MIXED as the average across Months 4-6.

Mean change from baseline to LOCF endpoint in the 6-month treatment phase for above quality of life measures will be evaluated using the ANCOVA model as described in Section 5.5.10.1.

The MSQ Role Function Restrictive domain responders and MIDAS responders will be analyzed using GLIMMIX. The threshold for MSQ Role-Function Restrictive Domain Response will be derived as outlined in "Statistical Analysis Plan for Psychometric Properties of the MSQ v2.1 Role Function-Restrictive Domain." The threshold for MIDAS response will be a 50% improvement from baseline in MIDAS total score.

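### MIDAS response is >50% improvement in SAP 5.4.3.2 but ≥50% in protocol Table CGAH.1 and SAP Table 4.3, so a patient at exactly half of baseline can be counted either way

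*SAP*

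**What the plan says.** The MIDAS responder rule is stated in four places.

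- **Protocol Table CGAH.1, tertiary objectives:** an inclusive rule (≥50%) on the MIDAS total score.
- **SAP 4.3, Table 4.3, exploratory objectives:** the same inclusive rule, "≥50% improvement in MIDAS total score".
- **SAP 5.4.3.2, derivation of the MIDAS measures:** a strict rule, "The MIDAS responders are defined as patients with >50% improvement in the total MIDAS score". The same section makes the responder indicator an analysis value.
- **SAP 5.5.11, quality-of-life analyses:** "The threshold for MIDAS response will be a 50% improvement from baseline in MIDAS total score", with no inequality sign. This section also names the model: "The MSQ Role Function Restrictive domain responders and MIDAS responders will be analyzed using GLIMMIX".

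On the scale itself, SAP 5.4.3.2 says: "Each question is answered as a numeric number of days during the past 3 months of assessment, ranging from 0 to 90". It adds: "The answers to all 5 questions will be added up to a total MIDAS score".

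The revision history in SAP section 3 records a MIDAS clarification on imputation and changes to the MSQ responder definition. It records no change to the MIDAS threshold.

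**The concern.** The two signs cannot both be programmed. The section with the strict sign is the one a programmer would open to build the indicator, and SAP section 3 says the SAP supersedes the statistical plans in the protocol. A literal implementation would therefore count as non-responders some patients whom the declared endpoint counts as responders.

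MIDAS totals are sums of day counts, so landing exactly on 50% is possible in a way it would hardly be on a continuous scale. At stake is a reported responder proportion that depends on which section was followed. The choice between sections would be left open until the data are analysed.

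**Working it through.** The documents give no stated figure for MIDAS response (no sample size, power or expected rate), so there is nothing to reproduce. The check covers the boundary arithmetic and then an illustration of its size.

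**1. Who changes status.** Let B be the baseline total and F the follow-up total. Improvement is 100 × (B − F)/B for B > 0. Setting this equal to 50 gives F = B/2. Below that value both rules say responder, above it both say non-responder, and only at F = B/2 do they disagree.

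- B = 20, F = 10: 100 × 10/20 = 50. The strict rule says no and the inclusive rule says yes.
- B = 21, F = 10: 100 × 11/21 = 52.4. Both say yes.
- B = 21, F = 11: 100 × 10/21 = 47.6. Both say no.

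**2. Which baselines can tie.** Five items of 0 to 90 give totals up to 5 × 90 = 450. If entries are whole days (natural for a count of days, though not stated outright), only even totals can be halved exactly. That is 450/2 = 225 of the 450 possible positive totals. A baseline of zero leaves the percentage undefined under either sign and is a separate matter.

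**3. How often, under assumptions.** All inputs here are assumed. Each simulated patient has an underlying day rate drawn from a gamma distribution (mean 15, 30, 45 or 60; shape 1.5 or 3). B is Poisson at that rate. F is Poisson at that rate times a mean follow-up/baseline ratio (0.4, 0.5 or 0.7) times gamma variation with mean 1 and shape 2. There were one million patients per setting, and those with B = 0 were dropped. The tie share is the proportion meeting ≥50% minus the proportion meeting >50%.

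| Assumed mean baseline total | Tie share over the six settings | Of 611 |
|---|---|---|
| 15 | 3.72% to 4.57% | 22.7 to 27.9 |
| 30 | 2.10% to 2.93% | 12.9 to 17.9 |
| 45 | 1.45% to 2.21% | 8.8 to 13.5 |
| 60 | 1.13% to 1.74% | 6.9 to 10.6 |

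For example, at mean 30, shape 1.5 and ratio 0.5, the responder rate is 60.1% under ≥50% and 57.1% under >50%. The unrounded gap is 2.93 points.

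**4. Denominator.** The 611 is the plan's own number of expected completers (protocol 9.1, SAP 5.2): 825 × (1 − 0.26) = 610.5. Applying the shares to all 611 treats every completer as having a positive baseline and a MIDAS total at the visit.

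**5. Treatment difference.** Let t be the tie share in an arm. Changing the sign moves that arm's rate by t, so the active-minus-placebo difference moves by t(active) − t(placebo). This is never larger in size than the larger of the two shares. No arm-level comparison was simulated, so no figure is given for it.

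**The case against.** **The sign may be a reading artefact.** In text read from a PDF, a ≥ can lose its underline. In SAP Table 5.8 the QRS upper limit appears as an underlined >, while SAP 5.5.12.1.4 gives the same cut-off as ≥120. The strict sign in 5.4.3.2 could have arisen the same way. This stands as a reason to check the page first. It is not decisive, because ≥ survives in Table 4.3, in Table 5.1 and in the migraine-day responder rule. Even if it is an artefact, 5.5.11 still lacks a sign.

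**The intended rule can be recovered.** Reaching a 50% threshold ordinarily includes 50% itself, and the migraine-day responder rule in SAP 5.4.1 is inclusive. This makes ≥50% the likely intention. It does not remove a contrary statement in the derivation section.

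**It matters little.** MIDAS response is tertiary in the protocol and exploratory in the SAP, and protocol 9.4.2 says of endpoints outside the primary and key secondary family: "There will be no adjustments for multiplicity for analyses of other endpoints". The other-secondary MIDAS endpoint is change in total score and items at Month 6, which uses no threshold. All of this stands and fixes the point as minor.

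**Stronger readings that the documents do not support.** A reader might infer that exact halving is a common outcome. No odd total can tie, and nothing in the plan gives a MIDAS mean, spread or expected improvement. A reader might also scale the shares to all randomized patients ("The study will enroll approximately 825 patients"), which gives 0.0113 × 825 = 9.3 to 0.0457 × 825 = 37.7. That denominator ignores the assumed 26% discontinuation. Finally, a reader might infer a bias in the treatment comparison. Boundary patients move the same way in every arm, and no change in the contrast has been shown.

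**Conclusion.** As the text reads, the definitions conflict: strict in SAP 5.4.3.2, inclusive in protocol Table CGAH.1 and SAP Table 4.3, and unsigned in SAP 5.5.11. Following 5.4.3.2 literally would misclassify, against the declared endpoint, exactly those patients at half of an even, positive baseline total.

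Rounded, the simulated share is about 1% to 5% of patients with data at a visit, and each arm's responder rate would be lower by that amount under the strict rule. The range rests on whole-day entries and on assumed gamma-Poisson totals without rounding to multiples of five or ten. It is an illustration, not a prediction for this trial.

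The sample size, type I error control, and primary and key secondary analyses are unaffected. This is a minor correction, conditional on the printed sign in 5.4.3.2 being confirmed.

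**What to change.** 1. Check the sign in SAP 5.4.3.2 against the original page.
2. If it is strict, replace it so that the section reads ≥50% improvement from baseline, in line with protocol Table CGAH.1 and SAP Table 4.3.
3. In SAP 5.5.11, state the same ≥50% improvement from baseline, whatever the check shows.

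This needs no new data, no change to sample size and no protocol amendment, since it brings the SAP back to the protocol's endpoint. Protocol 9.2 allows SAP changes only before unblinding, so it belongs in the SAP before interim analysis #2. If that point has passed, the clinical study report should say which sign was programmed.

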5.4.4. Safety Endpoints

Safety endpoints consist of the incidences of treatment emergent adverse events (TEAEs), serious adverse events (SAEs) and adverse events (AEs) leading to discontinuation, vital signs (blood pressure, pulse, and body temperature), weight, suicidal ideation and behaviors assessed by solicited questioning using the Columbia-Suicide Severity Rating Scale (C-SSRS), electrocardiograms (ECGs), and laboratory measures (chemistry, hematology, and urinalysis).

5.4.5. Immunogenicity Endpoints

Immunogenicity endpoints consist of the incidences of anti-drug antibodies (ADAs) in all trial participants at baseline (pre-existing ADAs), and in all trial participants at post-baseline (treatment emergent ADAs). An additional endpoint is the incidence of neutralizing antibodies (NAbs) present in those trial participants with ADAs.

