# 9.7.2. Subgroup Analyses

Subgroup analyses will be performed for the primary efficacy measure (change from baseline in the number of migraine headache days) separately for each of the subgroup populations listed in Table CGAH.4. Subgroup analyses will be conducted only for the ITT patients in Study Period III

Each of the subgroup analyses for the primary measure of change from baseline in the number of migraine headache days will be conducted using MMRM. The same MMRM model described in Section 9.4.1 will be used, with terms of subgroup, subgroup-by-treatment, subgroup-by-month, and subgroup-by-treatment-by-month interactions added as additional co variates.

Table CGAH.4. Definition of Subgroup Variables

Subgroup Variable	Categories								
• Sex	Male, female								
Racial Origin (combine those with	American Indian / Alaskan Native								
less than 10%)	Asian								
	Black / African American								
	Native Hawaiian / Pacific Islander								
	White								
	Multiple								
Ethnicity	Hispanic or Latino								
	Not Hispanic or Latino								
• Region	Defined in the statistical analysis plan (SAP)								
Baseline number of migraine	2 levels of baseline migraine frequency :								
headache days	• <8 migraine headache days								
	• ≥8 migraine headache days								
Treatment-resistant status	Treatment-resistant status about whether a patient has failed 2 or								
	more prophylactic treatments (Yes or No)								
Having aura or not (during baseline	Yes or No								
period)									
Baseline anti-drug antibody status	Any confirmed positive anti-drug antibody at baseline (Yes								
	versus No)								
Neutralizing anti-drug antibody	Any positive neutralizing anti-drug antibody time point (Yes								
status	versus No) – note that neutralizing ADA assays are performed								
	only on confirmed-positive anti-drug antibodies.								
Treatment-emergent anti-drug	Any treatment-emergent anti-drug antibody (Yes versus No)								
antibody status									

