5.5.12.1.6. Immunogenicity

To evaluate the changes in immunogenicity data (Anti-LY2951742 Antibody (hereafter "Anti-Drug Antibody (ADA)," Neutralizing ADA (hereafter "Neutralizing Antibody (NAb)") after treatment, the following statistical analyses are planned for comparison between treatment groups.

- The incidence of ADA positive and NAb Positive during baseline.
- The incidence of treatment-emergent ADA (TE ADA) between treatment groups will be summarized for Study Period III. The incidence of TE ADA during Study Periods III and IV combined will be summarized. The baseline and post-baseline definitions for each study period is shown in Table 5.5. Treatment-emergent ADA will be defined as any of the following:
 - o a negative baseline result and a positive post-baseline ADA result with a titer ≥20. This is also called treatment-induced ADA.
 - a positive baseline result and a positive post-baseline ADA result with a ≥4-fold increase in titers (for example, baseline titer of 10 increasing to ≥40 post-baseline).
 This is called treatment-boosted ADA.
- The incidence of TE-ADA and NAb Positive combined between treatment groups will be summarized for the same time periods as planned for the incidence of TE ADA.
- The following will also be created:
 - Listing of subjects with TE ADA at any time during study, NAb Status will also be displayed.
 - Listing of subjects with ADA detected at any time during study, excluding subjects with TE ADA.
 - o Line plot of ADA titers over time for each subject with TE ADA at any time.
 - Listing of subjects with TEAEs for hypersensitivity events or TEAEs related to injection sites for subjects with ADA present at any time.

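### After baseline, SAP 5.5.12.1.6 summarises neutralizing antibodies only jointly with treatment-emergent ADA, which is narrower than the endpoint in SAP 5.4.5

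*SAP*

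**What the plan says.** SAP 5.4.5 names two ADA endpoints: ADA at baseline, described as pre-existing, and ADA "in all trial participants at post-baseline (treatment emergent ADAs"). It then adds the neutralizing-antibody endpoint: "An additional endpoint is the incidence of neutralizing antibodies (NAbs) present in those trial participants with ADAs". That sentence sets no titre threshold.

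SAP 5.5.12.1.6 plans two NAb summaries. The first is "The incidence of ADA positive and NAb Positive during baseline". The second is "The incidence of TE-ADA and NAb Positive combined between treatment groups will be summarized for the same time periods as planned" for TE ADA, that is, Study Period III, and Study Periods III and IV combined. TE ADA is either "a negative baseline result and a positive post-baseline ADA result with a titer ≥20" or "a positive baseline result and a positive post-baseline ADA result with a ≥4-fold increase in titers".

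Of the listings in that section, the one for TE ADA subjects is to show NAb status. The one for subjects with ADA but without TE ADA does not mention it. SAP 5.5.12 names ADA and NAb among the safety items to be summarised, without a definition or denominator.

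Protocol Table CGAH.1 (repeated in SAP Table 4.2) has a secondary objective on how both ADAs and neutralizing ADAs develop and what follows from them. It is not limited to TE ADA.

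**The concern.** The endpoint and its analysis describe different sets of patients. The endpoint asks how often ADA-positive participants have a neutralizing antibody. The post-baseline analysis asks how often participants have both a neutralizing antibody and an ADA titre that passes the TE rule. Whether an antibody neutralizes is a different property from its titre, so a patient can acquire the first without meeting the second.

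At stake is whether the post-baseline NAb figure for a monoclonal antibody, in a trial that Protocol 2.2 calls pivotal, is the quantity the SAP says it will report. Because the joint condition is a subset, its count can only equal or fall below the count of participants with any post-baseline NAb.

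**Working it through.** **1. Reproduce the SAP's own example.** For treatment-boosted ADA, 5.5.12.1.6 illustrates a baseline titre of 10 rising to at least 40. Check: 10 × 4 = 40. It reproduces.

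**2. Apply the rule to a grid.** The rule is: baseline negative, TE if post-baseline titre ≥ 20; baseline titre b, TE if post-baseline titre ≥ 4 × b. The titres 10, 20, 40, 80 and 160 are assumed for illustration; they are not study data.

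| Baseline | TE threshold | Positive after baseline but not TE ADA | TE ADA |
|---|---|---|---|
| Negative | 20 | 10 | 20, 40, 80, 160 |
| 10 | 4 × 10 = 40 | 10, 20 | 40, 80, 160 |
| 20 | 4 × 20 = 80 | 10, 20, 40 | 80, 160 |
| 40 | 4 × 40 = 160 | 10, 20, 40, 80 | 160 |

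Every baseline state leaves some ADA-positive post-baseline results outside TE ADA.

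**3. Trace two patients through the planned outputs.** Neither is TE ADA at any post-baseline sample.

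| Output in SAP 5.5.12.1.6 | Patient A: baseline ADA titre 10, NAb negative; later at most 20, NAb positive | Patient B: baseline ADA negative; later at most 10, NAb positive |
|---|---|---|
| Baseline ADA positive | Counted | Not counted |
| Baseline NAb positive | Not counted | Not counted |
| TE ADA incidence | Not counted | Not counted |
| TE ADA and NAb positive | Not counted | Not counted |
| Listing of TE ADA, with NAb status | Absent | Absent |
| Listing of ADA without TE ADA | Present, NAb status not stated | Present, NAb status not stated |

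Patient A has pre-existing ADA and so belongs to the 5.4.5 population on any reading, yet enters no NAb summary. Patient B belongs to it only if 5.4.5 covers any post-baseline ADA.

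**4. Limits of the gap.** The TE definition does not require the NAb and the titre rise to occur in the same sample. A patient is missed only if no post-baseline sample in the period meets the TE rule. Baseline NAb is summarised.

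**5. Size.** The number missed through Patient A's route in a dose arm is n × (share with pre-existing ADA) × (share of those turning NAb positive without ever having a fourfold rise). Only n is given: a target of 206 per dose arm. With an assumed 5–15% for the first share:
- second share assumed 25%: 206 × 0.05 × 0.25 = 2.6, to 206 × 0.15 × 0.25 = 7.7 patients;
- second share assumed 2%: 206 × 0.05 × 0.02 = 0.2, to 206 × 0.15 × 0.02 = 0.6 patients.

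The answer is set by the guess, so no count is claimed.

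**The case against.** The strongest reply is that 5.4.5 does not say all participants with ADAs. The sentence before the NAb endpoint equates post-baseline ADA with treatment-emergent ADA, so the endpoint may refer back to two groups only: pre-existing ADA and TE ADA. Section 5.5.12.1.6 reports NAb for both, and its stated purpose is change after treatment, which suits a treatment-emergent rule. This stands in part: it makes Patient B arguable. It does not reach Patient A, who has pre-existing ADA and whose NAb appears only after baseline.

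The word for the joint row might also be read as either condition rather than both. That would not help, because NAb incidence could not then be separated from TE ADA incidence.

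A reader might go further in four ways that the documents do not support.
- *That NAb results exist for every ADA-positive sample.* Protocol Table CGAH.4 says "neutralizing ADA assays are performed" only on confirmed-positive ADA. That limits who may be tested; it does not say all are. Protocol 8.8.1 makes neutralization testing optional.
- *That the plan should count newly NAb-positive patients, and that a boosted patient already NAb positive at baseline is wrongly included.* Neither section requires a NAb to be new.
- *That the active arms are understated relative to placebo.* The rule applies to every arm, and no direction of between-arm bias can be shown.
- *That several patients per arm are lost.* The inputs for such a figure are not in the documents.

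Other outputs also soften the effect. Subjects without TE ADA are listed, and the listing of hypersensitivity and injection-site events covers anyone with ADA at any time.

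**Conclusion.** The point holds in a limited form. SAP 5.5.12.1.6 contains no post-baseline NAb summary that matches the endpoint in SAP 5.4.5. Patients with pre-existing ADA who become NAb positive after baseline and never have a fourfold titre rise are left out on either reading. Baseline-negative patients with titres below 20 are left out as well if 5.4.5 covers any post-baseline ADA.

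The conclusion rests on the text alone and on reading the joint row as requiring both conditions. How many patients are affected cannot be derived from the documents and could be negligible. Type I error, power, the primary analysis and the key secondary analyses are unaffected. It is a modest correction to a descriptive safety table, worth making because the SAP otherwise does not deliver its own endpoint.

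**What to change.** In SAP 5.5.12.1.6, for Study Period III and for Study Periods III and IV combined:
- add the incidence of NAb positive at any post-baseline sample among participants with ADA, regardless of TE ADA status, based on the NAb results available;
- show beside it the number of ADA-positive participants who were tested for NAb, since testing of all of them is not assured;
- keep the existing row for TE ADA with NAb as a subset of the new row;
- show NAb status in the listing of ADA-positive subjects without TE ADA.

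If the sponsor means the endpoint to cover only pre-existing and treatment-emergent ADA, 5.4.5 should say so. The new row is still needed for patients with pre-existing ADA.

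Cost: a short wording change, one table row per period and one listing column, with no new sampling. The reported NAb incidence may be slightly higher.
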